PHASE II. To evaluate the preliminary impact of 2VIDA! compared to the standard-of-care for COVID-19 vaccination services among Latinx and AA adults >16 years (N=1000) in San Diego. During Phase 2 we will offer the COVID-19 vaccine at the participating SYH community health centers and mini-vaccination stations that will be set-up in these communities (only intervention sites) as part of the intervention efforts (i.e., research activities) to increase access and uptake of the COVID-19 vaccine. We have identified various open spaces (e.g., public parks) in these communities to set-up the vaccination stations. SYH is currently offering the vaccine in their facilities as part of their standard of care. It is available to everyone who is eligible according to the state guidelines and does not depend on participating in this study. However, as part of 2VIDA! we will add these mini-vaccination stations to increase access to the vaccine (e.g., open after 5:00pm and on the weekends). Furthermore, data will be collected to assess individual, social, and contextual factors related to access, acceptance, and uptake of the COVID-19 vaccine including: a) sociodemographic characteristics; b) characteristics associated with social marginalization (e.g., homelessness, food insecurity); c) access to and utilization of health care; d) vaccination history, interest, hesitancy and uptake; e) perceptions of the COVID-19 vaccine (e.g., fears, myths, etc.); f) general health; and h) trust in government, research, and social agencies; i) satisfaction with 2VIDA! at baseline and 4-week follow-up. The survey will last approximately 20 minutes and will be self-administered in both English and Spanish. Following the survey participants will be offered the COVID-19 vaccine and the SYH staff will help them set-up an online appointment onsite for the 2nd dose (1 month follow-up) and will be asked to complete a 5 min survey during the follow-up visit. SYH has trained medical staff and a strict protocol for the storage, handling, and application of the vaccine. UCSD staff will not be involved in this process. Furthermore, participants will be asked to provide separate written consent in order to receive the vaccine that will be conducted by SYH staff. Additionally, two focus groups (FGs) will be conducted with members of Latinx and AA communities (n=8-10 participants per group) to obtain feedback on implementation and ways to improve future sustainability and scalability for future vaccination efforts among vulnerable underserved communities. FGs will be transcribed and reviewed for themes specific to 2VIDA! including personal and structural barriers to medical accurate information and the COVID-19 vaccine, benefits, challenges, feasibility, and scalability.

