
Mini-vaccination stations. We will set-up mini-vaccination stations in the parking of three public parks in the selected intervention sites to support the SYH community health centers. We will set-up signs with the *2VIDA!* project for participants to identify (e.g., same logo and illustrations used during Phase 1) and tent-lined lanes for eligible recipients to drive up. Research assistants will confirm eligibility with potential study participants via verbal assessment of the following inclusion criteria: 1) age 16 years or older; 2) identify as Latinx and/or AA; 3) biologically male or female; 4) be a resident of one of the three communities selected for the intervention (National City, Lincoln Park, Logan Heights, Valencia Park, San Ysidro); 5) literate in English or Spanish; 6) no known history of severe allergic reactions to any components of the vaccine; 7) no history of immune disease; 8) not be pregnant; 9) no plans to move from the area in the following 30 days; 10) able to provide voluntary informed consent; and 11) able to provide complete contact information for themselves (email and phone number) and two additional contact individuals for follow-up. Inside their car they will complete the 10-15 min. survey, receive the COVID-19 vaccine, and pull aside for a 15-minute observation period. We will also set-up additional tents with portable chairs at least 6 feet apart for participants who do not own a vehicle and want to receive the vaccine at the mini-stations. The stations will be opened Monday-Sunday from 7:00am-7:00pm based on the recommendations from our community partners (e.g., some individuals work early/late shifts). We will have two options for the vaccine – a one shot or a two-shot vaccine and the participants will select what type of vaccine they prefer. The vaccines will be available on a first come first-serve basis. For individuals who select a two-shot vaccine, the study staff will schedule the appointment for the participants on site when they receive the 1st dose of the vaccine (as they are waiting during observation period) and give them the date (confirmation). We will use the NextGen program to schedule the follow-up appointments for these participants. For participants who select a one-shot vaccine, they will be reminded that they will receive a text message and/or a link via email (based on their preference) to complete a follow-up survey in 4-weeks. Participants who select a two-shot vaccine will be asked to complete the follow-up survey (4-weeks) when they return for their second shot (during the observation period). We have noticed that percentage of our population has low digital literacy levels and/or limited access to internet or digital technologies which has made enrollment and follow-up challenging. In order to address these barriers, we are proposing to utilize Computer Assisted Telephone Interviewing (CATI)²⁰ and videoconferencing and screen sharing (VCSS).²¹ Both tools have been successfully used for many years in public health as well as by our community partner (SYH) on other similar federal-funded research projects. During enrollment, we would provide the participants with the option to complete the follow-up survey utilizing CATI or VCSS if they require assistance or have limited access to digital technologies. If they chose CATI or VCSS, following the completion of the follow-up survey we would send the incentive via a unique link similar to the follow-up for other participants. The entire team has been trained on these two platforms and would only be used for follow-up. Additionally, SYH will create a temporary patient ID for them and enter them in the system to schedule their second appointment. This is the software program that SYH is currently utilizing to follow-up for vaccine appointments. We believe that utilizing SYH existing infrastructure will allow sustainability and scalability of *2VIDA!*! The participants who select a two-shot vaccine will receive an email or automated

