receive the 2nd dose). The baseline survey will take approximately 20 minutes and the follow-up survey last 10 minutes, both will be self-administered (tablet). The research staff will be available in case the participants don't understand a question or need help with any aspect of the survey. We will also have Wi-Fi hotspot and mobile printers on site at the mini-vaccination stations for participants who would like to take a copy of the digital consent form and access to printers in the participating health centers. Following survey completion, participants will be eligible to receive the COVID-19 vaccine if they provided written informed consent (paper). Although participants would have already been screened for eligibility, the research assistants from SYH will confirm again that they do not have any known history of severe allergic reactions to any components of the vaccine, no history of immune disease, and not be pregnant. As previously mentioned, individuals may also receive the vaccine even if they choose not to participate in the study. Registered nurses from SYH will proceed to apply the COVID-19 vaccine and as previously mentioned, will observe the participant has no reaction for 15 minutes. SYH will follow strict vaccination protocols (based on the FDA and CDC COVID-19 recommendations and guidelines)^{1,7} and will report all vaccine administration errors, all serious adverse events following administration of the COVID-19 Vaccine to the IRB and to the Vaccine Adverse Event Reporting System (VAERS) and [name] will report to the IRB and NIH if warranted. Likewise, if an individual who received the 1st dosage of the vaccine at one of the control sites is seeking to receive the 2nd dosage of the vaccine at the intervention site or mini-vaccination station, they will be placed on a wait-list and contacted by our study staff towards the end of the day if there are available dosages due to the no-shows. Alternately, if they don't wish to be on the wait list we can schedule an appointment for them to the SYH community health center location that is most convenient for them.

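### The two-dose follow-up survey is by default taken at the dose-2 visit, and no survey route is given for persistent no-shows or decliners, so they are liable to be selectively missing from the 4-week survey outcomes

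*Protocol*

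**What the plan says.** **Survey routes.** For two-dose participants, Protocol Section 8 (Mini-vaccination stations) says: "Participants who select a two-shot vaccine will be asked to complete the follow-up survey (4-weeks) when they return for their second shot". Section 8 (Phase II), Section 9 and Section 12 also place the follow-up survey at the second dose. One-shot recipients need no visit: "they will receive a text message and/or a link via email (based on their preference) to complete a follow-up survey in 4-weeks". At enrollment, participants are also given the "option to complete the follow-up survey utilizing CATI or VCSS if they require assistance or have limited access to digital technologies" (telephone interview, or video with screen sharing).

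**No-shows and decliners.** For a missed second dose, Section 8 provides for contacting the participant's two named contacts and rebooking the dose; no survey step is mentioned. The baseline survey comes first and the vaccine second: "Following the survey participants will be offered the COVID-19 vaccine". A person can therefore be enrolled and then decline. No follow-up survey route is described for that person.

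**Outcomes.** Section 5 lists knowledge (H.1), receipt of vaccine (H.2) and series completion (H.3). Section 8 (Data Analysis) and the SAP make acceptance and series completion primary, and knowledge, access and hesitancy secondary. Neither names a data source, denominator or cut-off for completion. The nearest candidate is survey domain d) in Sections 5 and 8, which covers uptake at baseline and 4 weeks. H.3 defines completion only by reference to CDC recommendations, although the stations offer "a one shot or a two-shot vaccine and the participants will select what type of vaccine they prefer". The SAP mentions moderate attrition without a rate and gives no method for missing outcomes.

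**The concern.** For a two-dose participant, being surveyed at 4 weeks depends largely on returning for dose 2, which is the event that the primary completion outcome counts. People who miss dose 2 or refuse the vaccine are the ones whose knowledge and hesitancy the trial most needs to measure, and the written procedure gives them no default way to be measured.

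Two things are at stake:

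- **H.1 and hesitancy.** If completion differs by arm, as H.3 expects, and completers differ from non-completers in knowledge, a comparison of respondents is not a comparison of the randomised groups. Even with no bias between arms, the results under-represent non-completers.
- **H.3, conditionally.** If completion were read from survey respondents, most two-dose respondents would be completers by construction. If it came from complete vaccination records, this problem would not arise. The plan does not say which is intended.

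**Working it through.** The plan gives no completion rate, response rate or attrition rate, so there is no figure of its own to reproduce on this point. The only design input used is the effect size of .20, taken here as SD units. **Every other value is an assumption.**

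**Assumed inputs**
- c, completion among two-dose participants: 0.80 intervention, 0.70 control
- r, share of non-returners who answer the survey: 0, 0.2 or 0.5
- s, share choosing two doses: 0.7
- q, share of one-shot recipients who answer: 0.7
- D, knowledge gap between completers and non-completers: 0.5 SD, with one-shot recipients equal to completers
- all completers surveyed
- s, q and D the same in both arms

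**H.1 among the vaccinated.** The share of non-completers among respondents in an arm is

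f = s(1−c)r / [s(c + (1−c)r) + (1−s)q].

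The true non-completer shares differ by s × 0.10 = 0.07, which contributes 0.5 × 0.07 = 0.035 SD to the true difference. Hence

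observed = 0.20 − 0.035 + 0.5 × (f_control − f_intervention).

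Equal capture in both arms:
- r = 0: both f are 0, so observed = **0.165**.
- r = 0.2: f = 0.028/0.798 = 0.0351 (intervention) and 0.042/0.742 = 0.0566 (control), so observed = 0.165 + 0.5 × 0.0215 = **0.176**.
- r = 0.5: f = 0.070/0.840 = 0.0833 and 0.105/0.805 = 0.1304, so observed = 0.165 + 0.5 × 0.0471 = **0.189**.

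Unequal capture, using the same f values:
- r = 0.2 intervention, 0.5 control: 0.165 + 0.5 × (0.1304 − 0.0351) = **0.213**, too large.
- r = 0.5 intervention, 0.2 control: 0.165 + 0.5 × (0.0566 − 0.0833) = **0.152**, too small.

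If completion and capture are both equal, the f values are equal, the 0.035 term vanishes and observed = 0.20. If non-completers were the more knowledgeable group, the equal-capture error would change sign.

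**H.3 if read from two-dose respondents only.** p = c / [c + (1−c)r]; the true difference is +10 points.

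| r, intervention | r, control | Observed completion | Difference (points) |
|---|---|---|---|
| 0 | 0 | 100.0% vs 100.0% | 0 |
| 0.2 | 0.2 | 95.2% vs 92.1% | +3.1 |
| 0.5 | 0.5 | 88.9% vs 82.4% | +6.5 |
| 0.2 | 0.5 | 95.2% vs 82.4% | +12.9 |
| 0.5 | 0.2 | 88.9% vs 92.1% | −3.2 |

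From complete records on all enrolled participants the difference stays at +10. Decliners are not modelled in either calculation.

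**The case against.** **The plan does not exclude non-returners from follow-up.** Sections 5 and 8 set data collection at baseline and 4 weeks without conditioning on dose 2. Section 8 requires contact details from each participant, Section 11 pays an incentive for the follow-up survey without requiring a dose, and Section 15 keeps identifiers for re-contact. A two-dose participant who chose the telephone or video option could be surveyed without returning. This stands as far as it goes: a reader might infer that non-completers will certainly be unobserved, and the documents do not support that. But none of these provisions is tied to surveying a no-show or decliner, so liable to be missing is the accurate description.

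**There are good reasons for an on-site survey.** Section 8 reports "low digital literacy levels and/or limited access to internet or digital technologies which has made enrollment and follow-up challenging", and under Section 9 staff are on hand for those who "need help with any aspect of the survey". This stands, and the on-site option should be kept.

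**Direction is not established.** A reader might infer that the survey rule necessarily dilutes the effect. That follows only with equal capture in both arms and completers knowing more. Equal capture is not assured: Section 8 limits no-show tracing to 2VIDA! participants without saying whether that means both arms, and the one-shot choice is described only for the stations, which exist only at intervention sites. This objection stands in full.

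**H.3 may be sound.** SYH gives the doses, and "SYH will create a temporary patient ID for them and enter them in the system to schedule their second appointment". A reader might infer that the primary completion result is biased; that would require reading it from respondents, which no passage states. Nor does any passage say that one-shot recipients would be scored on a second dose. What remains is that the source is not named.

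**Conclusion.** The concern holds for the survey route. The stated default makes follow-up of two-dose participants depend largely on a primary outcome, no route is described for persistent no-shows or decliners, and no missing-data method is given. It should be fixed, and the remedy is inexpensive.

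The size and direction of bias cannot be taken from the documents. Under the assumed values, a true H.1 difference of 0.20 SD among the vaccinated is understated by about 6% to 17.5% with equal capture. The error is zero with equal completion and equal capture, and can go either way with unequal capture.

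The missing source for H.3, its definition by product and the record-linkage question are secondary clarifications, because SYH records could supply completion without this bias. Confidence is medium: the procedural gap is clear from the text, but its effect depends on rates that the plan does not give.

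**What to change.** 1. **Survey.** Keep the assisted survey at the dose-2 visit as an option. At a fixed time about 4 weeks after baseline, send the existing link, text or telephone survey to every participant in both arms who has not completed it, including no-shows and decliners, with the same survey tracing in both arms. Report response and survey mode by arm and by completion status. In the SAP, state how missing survey outcomes are handled, using recorded vaccination status.
2. **Uptake and completion.** State that both come from SYH vaccination records for all enrolled participants, supplemented by self-report for doses given elsewhere. Define completion for the product received, using the CDC reference already in H.3, with one cut-off common to both arms. Report the one-shot share by arm.
3. **Reconcile.** Section 14 says the survey code cannot be traced to identity, while Section 15 describes a list joining identifiers to the unique IDs. Settle which applies, and keep the SYH-side list until the cut-off. State whether 2VIDA! participants, in the no-show tracing text, means both arms.

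**Cost.** Protocol and SAP wording, an SYH records query, some extra survey contacts and slightly longer retention of the list. The link, telephone survey, scheduling system and incentive are already planned. It must be confirmed that consent covers record access; the consent pages were not in the reviewed text. Downsides are a possible difference between on-site and remote survey modes, and doses given outside SYH being known only by self-report. The vaccine schedule is unchanged.

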
mini-vaccination stations in communities highly impacted by the pandemic and identifying individual and structural barriers to COVID-19 immunization (Phase 2). Specific aims include:

Aim 1. To evaluate the preliminary impact of 2VIDA! compared to the standard-of-care for COVID-19 vaccination services among Latinx and AA adults ≥ 16 years (N=1000) in San Diego. We will use a 2-armed randomized controlled trial (RCT)* where Latinx and AA adults ≥ 16 years or older from six participating community health centers (CHC) and surrounding communities will be assigned to the 2VIDA! intervention (n=3 CHC; N=500 participants) or to the control site (e.g., standard of care) (n=3 CHC; N=500 participants). Data will be collected on a) sociodemographic characteristics; b) characteristics associated with social marginalization; c) access to and utilization of health care; d) vaccination history, interest, hesitancy and uptake; e) perceptions of the COVID-19 vaccine (e.g., fears, myths, etc.); f) general health; and h) trust in government, research, and social agencies, i) satisfaction with 2VIDA!; at baseline and 4-week follow-up. We hypothesize that at follow-up, compared to control participants, 2VIDA! participants will:

H.1. have increased knowledge about the COVID-19 vaccine (including medically accurate information, benefits, and risks);
H.2. more likely to receive the COVID-19 vaccine;
H.3. more likely to complete vaccine series (based on Centers for Disease Control and Prevention [CDC] recommendations).¹

Aim 2. To assess feasibility, acceptability, and intervention effects of 2VIDA! To assess feasibility and acceptability, we will utilize quantitative methods to track recruitment, condition assignment, participant retention, intervention implementation, and potential threats (e.g., contamination). We will also utilize qualitative methods to assess acceptability via focus groups with participants to understand potential for broad implementation (e.g., what components did they receive of the intervention, client satisfaction, linkage to COVID-19 services). To assess intervention effects, we will examine participant vaccination rates/completion across both groups.

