*Please note that only one community health center out of their 25 clinics is currently delivering 2VIDA! as a clinical program and all of their clinics are offering the vaccine on site (no mini-vaccination stations). For the purposes of this research, we will randomize 6 community health centers and their surrounding communities that are predominantly Latinx and AA to receive either 2VIDA! or the standard of care for vaccine delivery (i.e. no components of 2VIDA! will be deployed). In order to avoid contamination, the community health center where the 2VIDA! was developed (i.e., Chula Vista) and is currently being implemented as a clinical program will be excluded from this study. Additionally, SYH is currently offering the vaccine at their community health centers, however, there is low vaccine uptake, therefore we believe this study will help increase interest in the vaccine and address vaccine hesitancy by working with the community.

6. BACKGROUND AND SIGNIFICANCE (2-3 paragraphs maximum)

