
text reminder (based on their preference) 24 hours before their scheduled appointment for the 2nd dose. If a participant does not show-up to their appointment for the 2nd dose, we will contact the references that they provided (2 contacts) and reschedule their appointment. This is not an activity routinely done for COVID-19 vaccination efforts by SYH. This is only for *2VIDA!* participants and these tracking mechanisms have been effective in reducing attrition rates in our previous research efforts working with similar populations. Lastly, having participants scheduled for 2nd dosage will allow us to know how many vaccines we need to have available per day following the initial roll-out and avoid any shortages and/or unused dosages. We will follow the same process as with the first dosage, participants will drive up to the tent-lined lanes and inside their car or in tents and chairs (if they come by foot) they will complete the 5 min. survey, receive the 2nd shot of the COVID-19 vaccine, and pull aside for a 15-minute observation period.

The overall goal of this study is to provide medically accurate information and resources on COVID-19 and barriers to accessing the COVID-19 vaccine to increase acceptance, uptake and series completion among predominantly Latinx and African American communities that have been severely impacted by the pandemic. Therefore, individuals who do not meet the eligibility criteria to participate in this research project but are interested in receiving the COVID-19 vaccine will have access to receive the vaccine (just the same as study participants) at the mini-vaccination station or at the participating SYH community health center. We will also follow the same scheduling procedure for non-eligible participants. During the observation period after receiving the vaccine (15 minutes) SYH staff will schedule their appointment for the 2nd dose using the NexGen program at the mini-vaccination station or the SYH community health center that is most convenient for them. This will enable us to provide the ineligible individuals access to the vaccine and have sufficient amounts of the 2nd dose. We will follow the same process for an individual who received the 1st dosage of the vaccine at one of the control sites is seeking to receive the 2nd dosage of the vaccine at the intervention site or mini-vaccination station for non-research purposes.

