12. INFORMED CONSENT

At recruitment, research assistants will confirm eligibility with potential study participants via verbal assessment of the following inclusion criteria: 1) age 16 years or older; 2) identify as Latinx and/or AA; 3) biologically male or female; 4) be a resident of one of the three communities selected for the intervention (National City, Lincoln Park, Logan Heights, Valencia Park or San Ysidro); 5) literate in English or Spanish; 6) no known history of severe allergic reactions to any components of the vaccine; 7) no history of immune disease; 8) not be pregnant; 9) no plans to move from the area in the following 30 days; 10) able to provide voluntary informed consent; and 11) able to provide complete contact information for themselves and two additional contact individuals (for follow-up 2nd vaccine shot). These data will be recorded in the form of a Client Recruitment Log. Although pregnancy is not a contraindication for COVID-19 vaccination, working group members decided that vaccination of pregnant women may not be well received in our target communities. This decision was also made based on community leaders and CBO's recommendations. Research assistants will record data regarding eligibility and reasons for non-participation where applicable. We are requesting a waiver of parental consent for subjects enrolled in the study who are ages 16-17. We request that minors who are 16-17 are able to provide assent for themselves as this study poses minimal risk to the subjects. The biggest risk is the loss of confidentiality and appropriate measures will be taken by the research personnel to ensure all data is kept confidential. These include assigning a unique study ID to each participant, only sharing data with approved research personnel, and keeping all data on a password protected device.

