minutes. SYH will follow strict vaccination protocols (based on the FDA and CDC recommendations and guidelines)^{1,7} and will report all vaccine administration errors, all serious adverse events, cases of Multisystem Inflammatory Syndrome (MIS), and cases of COVID-19 that result in hospitalization or death following administration of the COVID-19 Vaccine to the IRB and to the Vaccine Adverse Event Reporting System (VAERS). Additionally, a detailed protocol has been developed by SYH to handle adverse events related to the COVID-19 vaccine, although none have occurred so far in the application of the COVID-19 vaccine. Staff members have been assigned specific responsibilities (e.g., if warranted, nurses will administer epinephrine or Benadryl and maintain an airway; outreach workers would call 911 and wait for the ambulance). The medical director of the study on behalf of SYH, [name], will be on call at all times, and a licensed nurse will manage all aspects of the COVID-19 vaccination phase. Additionally, project staff, will be responsible for immediately reporting any breaches of protocol, breakdowns in the consent process, violations of confidentiality of the data, complaints by participants or any serious problems or adverse events to the project coordinator who will file an incident report with [name]. [name] will collect any incident reports and communicate serious problems or adverse events to the UCSD HRPP, who will report to NIH if warranted.

Lastly, based on the intervention components and objectives, we do not foresee an increased risk of an individual receiving the 1st dose but not the 2nd dose as a result of participating in this project. The different *2VIDA!* individual and community research activities centered on providing health literacy and addressing vaccine hesitancy, as well as the reminders and tracking mechanisms in place (i.e., providing two additional contacts), we believe that participants from this research projects will be more likely to receive the 2nd dosage.

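### Tracing of dose-2 no-shows appears limited to the intervention arm, yet the 4-week survey is taken at the dose-2 visit, so follow-up ascertainment is likely to differ by arm

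*Protocol*

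**What the plan says.** The tracing step is in protocol Section 8, in the text on mini-vaccination stations: "If a participant does not show-up to their appointment for the 2nd dose, we will contact the references that they provided (2 contacts"), after which the appointment is rebooked. The section then makes three statements about it:

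- on routine care: "This is not an activity routinely done for COVID-19 vaccination efforts by SYH";
- on who receives it: "This is only for *2VIDA!* participants";
- on its effect: "these tracking mechanisms have been effective in reducing attrition rates in our previous research efforts working with similar populations".

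Three places bear on which arm that means. In Section 5 the hypotheses use the same term for the intervention arm: "We hypothesize that at follow-up, compared to control participants, 2VIDA! participants will". Section 8 places the mini-stations at intervention sites only. The notes on randomisation in Sections 5 and 8 give control clinics the "standard of care for vaccine delivery (i.e. no components of 2VIDA! will be deployed").

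Two other places do not separate the arms. Criterion 11 in Section 12 requires "two additional contact individuals (for follow-up 2nd vaccine shot") from potential participants at recruitment. Section 14 expects better second-dose receipt among the project's participants and gives this among its reasons: "the reminders and tracking mechanisms in place (i.e., providing two additional contacts), we believe that participants from this research projects will be more likely".

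The follow-up survey is tied to the same visit. Section 8 (Phase II and the mini-station text) has two-shot recipients complete it when they return for dose 2, and Sections 9 and 12 describe it the same way. One-shot recipients get a text or email link. Telephone or video completion is offered to those who need help or have limited digital access.

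Series completion is a primary outcome and knowledge a secondary one (Section 8, Data Analysis, and the SAP). The SAP allows for moderate attrition but gives no rate, no split by arm and no missing-data method.

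**The concern.** One action does two jobs. Bringing a no-show back for dose 2 raises series completion, and it also brings that person back to the place where the survey is taken. If it is done in one arm only, the arms differ in the care delivered, which is the purpose of the trial, and also in how completely they are measured, which is not.

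At stake are the outcomes that need a follow-up response: knowledge (H.1), hesitancy, and vaccination or completion where it is self-reported. The control arm would lose more of its two-shot no-shows than the intervention arm, so the two sets of respondents would not be selected in the same way. Series completion is exposed as well, because the plan does not say how it is established for someone who does not return.

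If the step were instead applied to everyone enrolled, controls would receive a completion aid that SYH does not normally give. The comparator would then no longer be standard of care as the protocol defines it. No section states which applies, so staff at control clinics have no clear instruction.

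**Working it through.** **The plan's own figure.** The plan states power of .90 for an effect of .20 at alpha .05. Reading .20 as a standardised mean difference, with 500 per arm and a two-sided test and ignoring clustering, power is 0.885 with no attrition, 0.851 at 10% and 0.807 at 20%. Two-sided 0.90 needs 526 per arm before attrition. The stated 0.90 with attrition is reached only under unstated choices, for example one-sided testing at about 14% attrition (429 per arm). The present point does not rest on this figure. The .20 serves only as a yardstick. Unequal retention costs little power in itself (0.841 at 90% v 85%); the issue is bias.

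**Inputs.** The documents give no no-show, recovery or retention rates. All of the following are assumptions:

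- share missing the dose-2 appointment: 20% in each arm;
- share of those who come back: 50% with tracing, 20% without;
- share of participants starting a two-shot series: w = 1 (the extreme case), equal in the arms;
- survey lost if the person does not come back;
- people lost score 0.3 to 0.5 SD lower on knowledge than people retained, with the same gap in both arms and no true effect.

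**Step 1, retention if only the intervention arm is traced.** Retention = 1 - missed × (1 - recovered).

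- Intervention: 1 - 0.20 × 0.50 = 0.90
- Control: 1 - 0.20 × 0.80 = 0.84

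The gap is 6 points, or 6w points if only a share w start a two-shot series.

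**Step 2, knowledge among respondents.** The retained mean exceeds the full-sample mean by gap × (1 - retention).

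| Gap | Intervention shift | Control shift | Bias | Share of .20 |
|---|---|---|---|---|
| 0.3 SD | 0.3 × 0.10 = 0.030 | 0.3 × 0.16 = 0.048 | -0.018 SD | 9% |
| 0.5 SD | 0.5 × 0.10 = 0.050 | 0.5 × 0.16 = 0.080 | -0.030 SD | 15% |

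The sign is against 2VIDA!, because the traced arm keeps more of its lower scorers. It would reverse if the people lost scored higher. With w = 0.5 the bias halves, to -0.009 to -0.015 SD.

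**Step 3, series completion with unrecorded counted as not completed.** Let s be the share of lost participants who in fact had dose 2 elsewhere, equal in both arms. The documents give no value, so the full range 0 to 1 is shown.

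- Recorded difference: 0.90 - 0.84 = 0.06
- True difference: (0.90 + 0.10s) - (0.84 + 0.16s) = 0.06 × (1 - s)
- Bias towards 2VIDA!: 0.06s, that is 0, 3 or 6 points at s = 0, 0.5 or 1

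At s = 0 the whole 6 points is a real gain from tracing. As s rises, the same recorded 6 points becomes an artefact of who was seen. Data collected only at the visit cannot tell these apart.

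**Step 4, the other reading.** If controls are traced too, their completion on the same inputs rises from 0.84 to 0.90. That takes 0.20 × (0.50 - 0.20) = 6 points out of the contrast among two-shot starters.

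**The case against.** The strongest reply is that the text is less ambiguous than it looks. The step is described in the mini-station paragraphs, stations exist only at intervention sites, Section 5 uses the same term for the intervention arm, and control clinics receive no 2VIDA! component. Tracing is then an intervention component, and more completed series is an effect of the intervention. This largely stands. A reader might infer that the protocol flatly contradicts its own comparator. It does so only on the weaker reading, which rests on Sections 12 and 14 being silent about arm.

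A reader might also infer a large retention gap, such as 90% v 75%. The documents give no rates to support one, and tracing is triggered only by a missed dose-2 appointment. With 20% missing and 50% v 20% recovered, the gap is 6 points at most. One-shot recipients and people with no dose-2 appointment are untouched. Nor does the knowledge bias suggest a false benefit on H.1: on the assumptions above it runs the other way.

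The plan also has other retention measures that its wording does not restrict to one arm: a $20 card for the follow-up survey (Section 11) and telephone or video completion (Sections 8 and 12). Aim 2 tracks retention and contamination. These will narrow or reveal an imbalance. They do not prevent it, because the extra route back to the survey would still exist in one arm only.

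Finally, it is not certain that control participants supply two contacts. Criterion 4 in the same eligibility lists speaks of the three communities selected for the intervention. However, it names the same five places that Section 10 gives as the locations of all six clinics, and Section 12 applies the list at recruitment without distinguishing arms.

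**Conclusion.** The point holds in a limited form. On the likelier reading, a non-routine step that the protocol itself credits with lowering attrition is given to one arm and feeds directly into the visit where the survey is taken. Unequal survey ascertainment is therefore the expected result of following the plan, though not a certain one. On the less likely reading, the comparator needs a different description. The sections do not settle which reading applies.

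The size is modest on the assumed inputs: retention of 90% v 84% at most, a knowledge bias of -0.018 to -0.030 SD (9% to 15% of the .20 target) against 2VIDA!, and 0 to 6 points in favour of 2VIDA! on series completion if unrecorded is counted as not completed. All of these shrink in proportion to the share choosing a two-shot vaccine. They depend on assumed rates, and the direction for knowledge depends on lost participants scoring lower. The documents do not support reading a higher completion rate in the intervention arm as bias in itself. The fault is that the effect and its measurement cannot be separated. The change should be made because it is cheap and one primary outcome is affected.

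**What to change.** 1. Stop the 4-week survey from depending on the dose-2 visit. For anyone in either arm without a survey at 4 weeks, use the two contacts from criterion 11 on the same schedule and with the same number of attempts, with a script that asks only for the survey and does not rebook doses. The follow-up survey already covers vaccine uptake, so it would also inform completion for people who did not return. Amend criterion 11 in Section 12, which now ties the contacts to the second shot; Section 8 already describes them more generally as for follow-up.
2. Report survey retention by arm.
3. Reconcile the randomisation notes in Sections 5 and 8, the mini-station text in Section 8, criterion 11 in Section 12 and the closing paragraph of Section 14. They should state whether dose-2 tracing and rebooking is a 2VIDA! component and which arm receives it, and the comparator should be described to match. Which arm that should be is for the investigators to settle.

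The cost is protocol wording, a call script and extra calls in the control arm. If contacts are not in fact collected at control clinics, collecting them there is a further small item. One downside remains: a survey call may prompt a few controls to return for dose 2.
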